7.4.1.6 Monitoring of Subjects with Adverse Events

Adverse events are recorded and assessed continuously throughout the trial (see Section 7.4.1.3) and are assessed for final outcome at the End-of-Treatment visit. After the End-of-Treatment visit, only AEs that are deemed attributable to trial drug by the Investigator should be documented until the Safety Follow-up visit.

All SAEs ongoing at the End-of-Treatment visit must be monitored and followed up by the Investigator until stabilization or until the outcome is known, unless the subject is documented as "lost to follow-up". In addition, all trial drug related SAEs occurring after End-of-Treatment visit and ongoing at the Safety Follow-up visit must be followed up in the same manner. Reasonable attempts to obtain this information must be made and documented. It is also the responsibility of the Investigator to ensure that any necessary additional therapeutic measures and follow-up procedures are performed.

7.4.2 Pregnancy and In Utero Drug Exposure

Only pregnancies considered by the Investigator to be related to trial treatment (eg, resulting from a drug interaction with a contraceptive medication) are considered to be AEs. However, all pregnancies with an estimated conception date during the period defined in Section 7.4.1.3 must be recorded by convention in the AE page/section of the eCRF. The same rule applies to pregnancies in female subjects and in female partners of male subjects. The Investigator must notify the Sponsor or designee in an expedited manner of any pregnancy using the Pregnancy Report Form, which must be transmitted according to the same process as described for SAE reporting in Section 7.4.1.4.

Investigators must actively follow up, document and report on the outcome of all these pregnancies, even if the subjects are withdrawn from the study.

The Investigator must notify the Sponsor or designee of these outcomes using the Pregnancy Report Form. If an abnormal outcome occurs, the SAE Safety Report Form will be used if the subject sustains an event and the Parent-Child/Fetus AE Report Form if the child/fetus sustains an event.

Any abnormal outcome must be reported in an expedited manner as described in Section 7.4.1.4, while normal outcomes must be reported within 45 days from delivery.

In the event of a pregnancy in a subject occurring during the course of the trial, the subject must be discontinued from trial medication immediately. The Sponsor must be notified without delay and the subject must be followed as mentioned above.

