5.3.1.1 Inclusion Criteria for Dose Escalation

- 1. Able and willing to give written informed consent and has signed the appropriate written informed consent form (ICF), prior to performance of any trial activities.
- 2. Eligible male or female subjects aged ≥ 20 years.
- 3. Histologically or cytologically proven metastatic or locally advanced solid tumors, for which no effective standard therapy exists or standard therapy has failed.
- 4. ECOG PS of 0 to 1 at trial entry.
- 5. Life expectancy \geq 12 weeks as judged by the Investigator.
- 6. Adequate hematological function defined by white blood cell (WBC) count $\geq 3 \times 10^9/L$ with absolute neutrophil count (ANC) $\geq 1.5 \times 10^9/L$, lymphocyte count $\geq 0.5 \times 10^9/L$, platelet count $\geq 75 \times 10^9/L$, and Hgb ≥ 9 g/dL (in absence of blood transfusion).
- 7. Adequate hepatic function defined by a total bilirubin level $\leq 1.5 \times \text{ULN}$, an AST level $\leq 2.5 \times \text{ULN}$, and an ALT level $\leq 2.5 \times \text{ULN}$. For subjects with liver involvement in their tumor, AST $\leq 5.0 \times \text{ULN}$, ALT $\leq 5.0 \times \text{ULN}$, and bilirubin ≤ 3.0 is acceptable.
- 8. Adequate renal function defined by an estimated creatinine clearance > 50 mL/min according to the Cockcroft-Gault formula or by measure of creatinine clearance from 24-hour urine collection.
- 9. Highly effective contraception (that is, methods with a failure rate of less than 1% per year) for both male and female subjects if the risk of conception exists (Note: The effects of the trial treatment on the developing human fetus are unknown; thus, women of childbearing potential and men must agree to use highly effective contraception, defined in Appendix 2 or as stipulated in national or local guidelines). Highly effective contraception must be used 30 days prior to first trial treatment administration, for the duration of trial treatment, and at least for 4 months after stopping trial treatment. Should a woman become pregnant or suspect she is pregnant while she or her partner is participating in this trial, the treating physician should be informed immediately.
- 10. Woman of childbearing potential must have a negative serum pregnancy test at screening visit and a negative serum or urine pregnancy test at Day 1 before dosing, if applicable.

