- 11. Highly effective contraception (that is, methods with a failure rate of less than 1% per year) for both male and female subjects if the risk of conception exists (Note: The effects of the trial treatment on the developing human fetus are unknown; thus, women of childbearing potential and men must agree to use highly effective contraception, defined in Appendix 2 or as stipulated in national or local guidelines). Highly effective contraception must be used 30 days prior to first trial treatment administration, for the duration of trial treatment, and at least for 4 months after stopping trial treatment. Should a woman become pregnant or suspect she is pregnant while she or her partner is participating in this trial, the treating physician should be informed immediately.
- 12. Woman of childbearing potential must have a negative serum pregnancy test at screening visit and a negative serum or urine pregnancy test at Day 1 before dosing, if applicable.

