7.4.1.3 Definition of the Adverse Event Reporting Period

The AE reporting period for safety surveillance begins when the subject is included into the trial (date and time of first signature of informed consent) and continues through the trial's End-of-Treatment visit, defined as 28 days (± 5 days) after last trial drug administration. After the

CONFIDENTIAL INFORMATION

End-of-Treatment visit, only AEs that are deemed attributable to trial drug by the Investigator should be documented until the Safety Follow-up visit, defined as 10 weeks (± 2 weeks) after the last trial drug administration.

Any SAE assessed as related to MSB0011359C must be reported whenever it occurs, irrespective of the time elapsed since the last administration of MSB0011359C.

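### The eCRF window for recording pregnancies ends 38 to 99 days before the required contraception period does, and the protocol leaves later notification and follow-up unclear

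*Protocol*

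**What the plan says.** **Contraception.** Protocol Sections 5.3.1.1 (criterion 9) and 5.3.1.2 (criterion 11) require highly effective contraception during treatment and "at least for 4 months after stopping trial treatment". The rule binds women of childbearing potential and men. The reason given is: "The effects of the trial treatment on the developing human fetus are unknown". Section 3.4 lists embryofetal toxicity among the important risks, and Section 3.4.6 classes it as an important potential risk.

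**Recording.** Section 7.4.2 requires entry on the adverse event page of the eCRF for "all pregnancies with an estimated conception date during the period defined in Section 7.4.1.3", and applies the same rule to female partners of male subjects.

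**The period referred to.** Under Section 7.4.1.3 adverse event reporting starts at consent and "continues through the trial's End-of-Treatment visit, defined as 28 days (± 5 days) after last trial drug administration". After that visit only events the investigator attributes to the drug "should be documented until the Safety Follow-up visit, defined as 10 weeks (± 2 weeks) after the last trial drug administration".

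**Notification.** Section 7.4.2 goes on: "The Investigator must notify the Sponsor or designee in an expedited manner of any pregnancy using the Pregnancy Report Form". That sentence carries no conception-date limit. Investigators must then follow up and report outcomes, but the text refers back to the pregnancies already mentioned without saying which of them are meant.

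**Scheduled checks.** The last scheduled pregnancy test is at the Safety Follow-up visit (Sections 7.1.5.1 and 7.4.4). Later contacts are quarterly and name survival and further tumor therapy (Section 7.1.5.2). They do not name pregnancy.

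**The concern.** The protocol asks subjects to avoid conception for at least 4 months after treatment because fetal effects are unknown, yet it borrows the adverse event reporting period as the conception window for eCRF recording. That period was written for another purpose and is shorter.

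Its end is also uncertain when applied to pregnancies. The extension to 10 weeks covers only adverse events attributed to the drug, and Section 7.4.2 says that most pregnancies are not adverse events at all. One site could stop at 28 days and another at 10 weeks, and each could defend its reading.

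What is at stake is how completely pregnancies conceived soon after exposure are found, for a risk the protocol itself lists as important. No efficacy or primary safety result depends on it.

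**Working it through.** No sample size, power or error rate is involved, and the plan states no figure for this point that could be reproduced. The check is date arithmetic.

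**Inputs**
- Contraception after treatment: at least 4 months (Protocol 5.3.1.1 and 5.3.1.2).
- Month length: 30.4375 days (SAP Section 9.5).
- End of general adverse event reporting: 28 ± 5 days, that is 23 to 33 days (Protocol 7.4.1.3).
- End of reporting of drug-attributed events: 10 ± 2 weeks, that is 56 to 84 days (Protocol 7.4.1.3).
- Assumption: stopping treatment is dated from the last dose.

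**Contraception period:** 4 × 30.4375 = 121.75 days.

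**Shortfall** = 121.75 − day on which the recording window closes.

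| Window closes at | Day | Shortfall (days) | Share of 121.75 days |
|---|---|---|---|
| End-of-Treatment, earliest | 23 | 98.75 | 81.1% |
| End-of-Treatment, nominal | 28 | 93.75 | 77.0% |
| End-of-Treatment, latest | 33 | 88.75 | 72.9% |
| Safety Follow-up, earliest | 56 | 65.75 | 54.0% |
| Safety Follow-up, nominal | 70 | 51.75 | 42.5% |
| Safety Follow-up, latest | 84 | 37.75 | 31.0% |

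No reading brings the shortfall to zero. Even with a month counted as 28 days (4 × 28 = 112) and the latest Safety Follow-up visit, 112 − 84 = 28 days remain.

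**Do existing contacts fall where they are needed?** Taking 12-week steps from a nominal End-of-Treatment visit, the first contact is near day 28 + 84 = 112 and the second near day 28 + 168 = 196. The first falls about 10 days before the 4 months end and the second about 74 days after. A question at both would cover conceptions up to day 122, including those not yet recognised at the first contact.

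**The case against.** A reader might infer that pregnancies conceived after week 10 are neither reported nor followed. The documents do not support that, for four reasons.

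- The conception-date limit is attached to the eCRF page entry. The notification sentence in Section 7.4.2 has no such limit and, taken literally, reaches later conceptions.
- Section 7.4.2 closes with a duty to notify the sponsor and follow the subject when a pregnancy occurs in the course of the trial. The trial ends 1 year after the last subject's last dose (Section 5.7). The context is stopping medication, but the wording is not confined to it.
- The inclusion criteria ask that the treating physician be told at once of a pregnancy in a participant or a participant's partner while participation lasts.
- Drug-related serious events are reportable at any time (Section 7.4.1.3), and a congenital anomaly is a seriousness criterion (Section 7.4.1.1.2).

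It is also fair to say that no section defines a post-dose fetal-risk period that recording was meant to match. The 4 months are a minimum for contraception and nothing more.

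All of this stands against a claim of lost pregnancies. It does not remove the narrower problem:

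- The notification sentence directly follows the conception-date rule and can be read as limited by it. If it is limited, later conceptions drop out of both routes. If it is not, the eCRF and the Pregnancy Report Form work to different windows.
- Every one of these duties depends on the site learning of the pregnancy, and no scheduled procedure after Safety Follow-up asks.
- The serious-event route needs a relatedness judgement and yields only abnormal outcomes, whereas Section 7.4.2 wants normal outcomes as well.

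**Conclusion.** The point holds in a limited form. It is certain that the eCRF recording window is shorter than the contraception period, by about 52 days (38 to 66) if it runs to Safety Follow-up and about 94 days (89 to 99) if it ends at End-of-Treatment. It is unclear, and should be made clear, whether notification and outcome follow-up continue beyond the Section 7.4.1.3 period.

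The figures rest on the SAP's month length and on dating the end of treatment from the last dose. The documents give no expected number of pregnancies, and none is assumed here.

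This is an inexpensive improvement in ascertainment and does not threaten the trial's conclusions. SAP Section 6.1 shows that the study report and its addendum are already approved and that no final analysis will follow. The practical value now lies in any remaining follow-up, in a roll-over trial (Protocol Section 5.6) and in reuse of this text. No view is taken on how long contraception should last.

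**What to change.** Reconcile Protocol Sections 5.3.1.1, 5.3.1.2, 7.4.1.3 and 7.4.2:

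- In Section 7.4.2, replace the cross-reference to Section 7.4.1.3 with one explicit conception-date window. It should reach at least from the first dose to the end of the post-treatment contraception period that the protocol states; the present start at consent can stay.
- Say that this window governs eCRF entry, Pregnancy Report Form notification and outcome follow-up alike, for female subjects and for partners of male subjects.
- In Section 7.1.5.2 and the schedules of assessments, add a question on pregnancy (subject or partner) to the existing 12-weekly contacts until that period has been covered. On nominal timing this means the first two contacts after End-of-Treatment.

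The cost is a few sentences of protocol text, one question at contacts that already take place and a little extra data entry. No new visit or test is needed.

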7.4.3 Clinical Laboratory Assessments

It is essential that the Sponsor be provided with a list of laboratory normal ranges before shipment of IMP. Any change in laboratory normal ranges during the trial will additionally be forwarded to the CRO and the Sponsor.

All routine laboratory analyses will be performed at a laboratory facility local to the investigational site and relevant results must be drawn and checked before administration of MSB0011359C. The report of the results must be retained as a part of the subject's medical record or source documents. However, an assessment for albumin for the HCC cohort at Screening should be performed centrally. Blood samples for the tests listed in Table 8 will be taken from non-fasted subjects during the Screening period, at the End-of-Treatment visit, and during the treatment period as specified in the Schedules of Assessments (Table 1 and Table 2). Complete blood count and core serum chemistry must be checked within 48 hours prior to each dose administration.

Serum electrophoresis (for dose escalation part only), ACTH, ANA, RF, free T4, TSH, and urinalysis will be assessed at the time points defined in the Schedules of Assessments (Table 1 and Table 2). If confirmation of a subject's postmenopausal status is necessary, an FSH level will also be performed at Screening, see Section 7.1.1.

N/N

 Table 8
 Required Laboratory Panel Tests

Full Chemistry	Hematology	
AFP (HCC cohort only)	Absolute lymphocyte count	
Albumin	ANC	
Alkaline phosphatase*	Hematocrit	
ALT*	Hemoglobin	
Amylase	Platelet count	
AST*	RBC count	
GGT	WBC count and differential count	
BUN/total urea*	RBC morphology**	
Calcium*	Reticulocytes	
Chloride*	MCH	
Cholesterol	Mean corpuscular volume	
Creatine kinase	MCHC	
Creatinine*		
CRP	Hemostaseology	
Glucose*	aPTT	
LDH	Prothrombin time/INR	
Lipase		
Phosphorus/phosphates*	Basic Urinalysis (dipstick, including macroscopic appearance,	
Magnesium*	bilirubin, blood, color, glucose, ketones, leukocyte esterase, nitrite, pH, protein, specific gravity, urobilinogen)	
Potassium*	Full urinalysis (dipstick plus microscopic evaluation) to be performed only at the Screening and End-of-Treatment visit.	
Sodium*	and a basic urinalysis prior to each administration of the IMP.	
Total bilirubin/indirect bilirubin*		
Total protein	Totality of binding ADAs	
Uric acid		
Triglycerides	ACTH, ANA, RF, TSH, and free T4	
Hormone		
FSH (if applicable)		

ACTH=adrenocorticotropic hormone; ADA=anti-drug antibody; AFP=alpha-fetoprotein; ALT=alanine aminotransferase; ANA=antinuclear antibody; ANC=absolute neutrophil count; aPTT=activated partial thromboplastin time; AST=aspartate aminotransferase; BUN=blood urea nitrogen; CRP=C-reactive protein; FSH=follicle stimulating hormone; GGT=gamma-glutamyltransferase; IMP=Investigational Medicinal Product; INR=international normalized ratio; LDH=lactate dehydrogenase; MCH=mean corpuscular hemoglobin; MCHC=mean corpuscular hemoglobin concentration; RBC=red blood cell; RF=rheumatoid factor; TSH=thyroid stimulating hormone; T4=thyroxine; WBC=white blood cell.

CONFIDENTIAL INFORMATION

N/V

^{*} Core serum chemistries. ** This test will be conducted in cases that a patient has anemia due to hemolysis or anemia of unknown etiology.

If a subject has a clinically significant abnormal laboratory test value that is not present at Baseline, the test will be repeated weekly and the subject will be followed until the test value has returned to the normal range or the Investigator has determined that the abnormality is chronic or stable. In addition, RBC morphology will be assessed in case of anemia onset caused by hemolysis, or other unknown causes.

7.4.4 Vital Signs, Physical Examinations, and Other Assessments

The ECOG PS will be assessed at Screening and at subsequent visits as indicated in the Schedules of Assessments (Table 1 and Table 2) and documented in the eCRF.

Body weight will be measured at Screening and at subsequent visits as indicated in the Schedules of Assessments (Table 1 and Table 2) and documented in the eCRF. Body height will be measured at Screening only.

A physical examination will be conducted and SpO₂ measured at Screening and at subsequent visits as indicated in the Schedules of Assessments (Table 1 and Table 2) and documented in the eCRF (detailed description in Section 7.1). Any abnormalities arising or worsening after the signing of the ICF should be documented in the eCRF Adverse Event section (see Section 7.4.1). Abnormal findings are to be reassessed at subsequent visits.

An ophthalmology examination including slit lamp evaluation inclusive of the anterior segment and with visual acuity should be conducted at Screening. At subsequent visits, eye signs and symptoms should be checked. If there are any clinically relevant findings, then an appropriate ophthalmology examination including slit lamp evaluation inclusive of the anterior segment and with visual acuity should be obtained within 2 days.

Digital 12-lead ECGs will be recorded at Screening and at trial visits as indicated in the Schedules of Assessments (Table 1 and Table 2) until Week 13 (Visit 10).

All newly diagnosed or worsening conditions, signs and symptoms observed since Screening, whether related to trial treatment or not, are to be reported as AEs.

For female subjects of childbearing potential, serum β -HCG pregnancy test will be carried out during the Screening period. A urine or serum β -HCG test will be performed once a month during the treatment period as indicated in the Schedules of Assessments (Table 1 and Table 2), at the End-of-Treatment visit, and at the Safety Follow-up visit. Results of the most recent pregnancy test should be available prior to the next dosing of IMP. Subjects who are postmenopausal (age-related amenorrhea \geq 12 consecutive months and if needed FSH > 40 mIU/mL [in the postmenopausal range] as outlined in Section 7.1.1), or who have undergone hysterectomy or bilateral oophorectomy are exempt from pregnancy testing. If necessary to confirm postmenopausal status, an FSH will be drawn at Screening.

CONFIDENTIAL INFORMATION

7.5 Pharmacokinetics

7.5.1 Dose Escalation Part

Pharmacokinetics parameters include area under the concentration-time curve (AUC), maximum serum concentration observed postdose (C_{max}), minimum serum concentration observed postdose (C_{min}), and terminal half-life ($t_{1/2}$) (for definitions, see Section 8.5.3.2). Blood samples for the analysis of serum concentrations of MSB0011359C will be drawn in all subjects according to the Schedule of Assessments (Table 3).

7.5.2 Expansion Part

Pharmacokinetics parameters will include C_{max} and C_{min} . Blood samples for the analysis of serum concentrations of MSB0011359C will be drawn in all subjects according to the Schedule of Assessments (Table 3).

7.5.3 Body Fluid

[figure not shown]
Whole blood (2.5 mL per sample) will be collected for PK assessments. Post-infusion samples should be drawn from a site other than the infusion site (ie, the contralateral arm) on the days of infusion. If the infusion is interrupted, the reason for interruption and the exact infusion times will be documented on the eCRF.

The total amount of blood taken during the first 8 weeks of the trial will not exceed the total of 300 mL and during the first 85 days will not exceed the total of 350 mL.

Further details will be summarized in the Laboratory Manual.

1

CONFIDENTIAL INFORMATION

7.7 Other Assessments

7.7.1 Anti-drug antibody Analysis

The blood sample for Baseline ADA analysis will be collected before trial treatment start. Further serum samples for ADA analysis will be collected as indicated in the Schedule of Assessments (Table 3). Whole blood (3.5 mL per sample) will be collected for ADA analysis at each sampling point.

57

Samples positive for ADAs will be re-analyzed to determine the titer.

The detection of antibodies to M7824 will be performed using a validated assay method with tiered testing of Screening, confirmatory, and titration. Confirmed positive antibodies may be tested for the presence of neutralizing antibodies and may be further characterized.

Further details will be summarized in the Laboratory Manual.

7.7.3 Health-related Quality of Life

For subjects in the GC, ESCC, and BTC expansion cohorts, symptom severity will be assessed using a generic question to assess severity of symptoms (PGIS) and using instruments for the assessment of cancer-specific symptoms (Table 2). Each of the instruments and the selected items for administration are described below.

PGIS: The PGIS is an in-house questionnaire to assess how the subject rates their overall symptom severity (How would you rate the overall severity of your symptoms over the past 7 days – none, mild, moderate, severe, very severe?). The PGIS will be administered in the GC, ESCC, and BTC expansion cohorts.

EORTC QLQ-C30: The EORTC QLQ-C30 is a 30-item patient-reported outcome questionnaire created to measure broad functioning, symptoms, and health-related quality of life issues across all types of cancers (Aaronson 1991). Each of these items is rated on a 4-point response scale (1 = not at all; 4 = very much). A subset of the EORTC QLQ-C30 items have been selected for administration to reduce patient burden while allowing for key tumor-related and metastasis-related symptoms to be assessed, as follows:

- GC: Fatigue (3 items)
- ESCC: Fatigue (3 items) and general pain (2 items)
- BTC: Fatigue (3 items)

EORTC QLQ-STO22: The EORTC QLQ-STO22 is a 22-item patient-reported outcome questionnaire created to measure functioning, symptoms, and health-related quality of life issues specific to stomach cancer (Vickery 2001). Each of these items is rated on a 4-point response scale (1 = not at all; 4 = very much).

• GC: Dysphagia (3 items), stomach pain (3 items), and early satiety (1 item)

[figure not shown]

EORTC QLQ-OES18: The EORTC QLQ-OES18 is an 18-item patient-reported outcome questionnaire created to measure functioning, symptoms, and health-related quality of life issues specific to esophageal cancer (Blazeby 2003). Each of these items is rated on a 4-point response scale (1 = not at all; 4 = very much).

[figure not shown]
- ESCC: Dysphagia (3 items) and reflux pain (2 items)
- **EORTC QLQ-BIL21**: The EORTC QLQ-BIL21 is a 21-item patient-reported outcome questionnaire created to measure functioning, symptoms, and health-related quality of life issues specific to cholangiocarcinoma and gallbladder cancer (Friend 2011). Each of these items is rated on a 4-point response scale (1 = not at all; 4 = very much).
- BTC: Stomach/back pain (3 items), early satiety (1 item), and itching (1 item)

EORTC QLQ-HCC18: The EORTC QLQ-HCC18 is an 18-item patient-reported outcome questionnaire created to measure functioning, symptoms, and health-related quality of life issues specific to HCC (Blazeby 2004). Each of these items is rated on a 4-point response scale (1 = not at all; 4 = very much). While not specifically designed for BTC, the EORTC QLQ-HCC18 includes two items that are a key symptom associated with BTC:

• BTC: Fevers (2 items)

M7824 (MSB0011359C) MSB0011359C in Metastatic or Locally Advanced Solid Tumors in Asia MS200647-0008

CONFIDENTIAL INFORMATION

CCI

